9 STATISTICAL CONSIDERATIONS

9.1 Statistical Plan & Sample Size Calculation

The acceptability of each screening modality will be assessed with the Impact of Events Scale (IES) scores, and the intrusiveness and avoidance subscales. We plan to recruit 40 subjects for the study.

Since the same subject will undergo treatment with each of the screening modalities, we anticipate that the scores generated will be correlated. We assume each pair of scores will have the same correlation. For the planned analysis, each IES score will be classified as low or high. High score will be defined as total IES score >38 .²⁵ A low score will be defined as a total IES score less than or equal to 38.

To compute power, for each of the three devices we specified the proportion of high scores as well as the correlation between observations within a subject. Estimating that 1% of the subjects undergoing sedated EGD group, 5% of those undergoing Cytosponge,²⁵ and 20% of those undergoing TNE will experience a high IES score, using a correlation of 0.3, and a sample size of 40, we specified a trivariate Binomial distribution. Random data were generated from such a distribution and Fishers Exact Test was computed from the data. This was done 10,000 times. The percentage of the 10,000 trials in which the Fishers Exact Test p-value was less than 0.05 provided our power estimate of 80% for a sample size of 40.

We will compare the median IES score for each modality using Kruskal-Wallis testing as well comparing the proportion of subjects with high IES scores for each modality using Pearson's chi-square testing. For the secondary objectives:

- **Secondary objective 1:** Median VAS score will be compared between the three modalities using Kruskal-Wallis testing
- **Secondary objective 2:** The proportion of subjects willing to repeat each test will be computed.
- **Secondary objective 3:** Subjects' preferred screening modality ranked highest will be measured as proportions. The proportion of the highest ranked screening modality will be computed.
- **Secondary objective 4:** Bivariate and multinomial logistic regression analyses will be used to identify factors such as patient discomfort, sex, and EGD indication influencing screening preference among the three modalities.

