Since we are recruiting patients from two separate pathways (described in Section 5.1), we plan to account for the differences by analyzing the two groups separately as well as the entire cohort as a whole to see if there is a statistically significant difference in results between the groups. In addition, we acknowledge that the results may be affected by carryover effect for subjects recruited via Pathway 1, but recruiting via this strategy makes this study feasible, and we will acknowledge this as one of the limitations.

All hypothesis tests that are deemed to be not statistically significant will be reported as being inconclusive.

All statistical estimates of population parameters will be tabulated along with corresponding standard errors, or confidence intervals (CI) to convey levels of precision and imprecision.

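### Section 9.1 allows a standard error, or an interval of unnamed type, for near-zero proportions; with 0 of 40 high EGD scores, the usual choices would show no uncertainty at all

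*Combined protocol and SAP*

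**What the plan says.** Section 9.1 dichotomises the primary instrument: "High score will be defined as total IES score >38". It plans to compare the proportion of high scorers across the three modalities, alongside a comparison of median scores. The planning rates are given in the power paragraph: "Estimating that 1% of the subjects undergoing sedated EGD group, 5% of those undergoing Cytosponge", and "20% of those undergoing TNE will experience a high IES score". A literature citation is attached to the Cytosponge figure; none is attached to the EGD figure. On size, the section says "We plan to recruit 40 subjects for the study".

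The end of the same section sets the reporting rule: "All statistical estimates of population parameters will be tabulated along with corresponding standard errors, or confidence intervals (CI"). The stated purpose is to show how precise or imprecise the estimates are. The rule covers every estimate, leaves the choice between the two measures open, and names neither a standard error formula nor an interval method. Section 9.1 also plans analyses of the two recruitment cohorts separately as well as together. Cohort sizes are not given; Section 5.1 says only that Cohort A is the main source and Cohort B is used if recruitment is difficult.

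**The concern.** A standard error, or a Wald interval built on it, is a poor measure of precision for a proportion near zero in a small sample. It fails completely at a count of zero, where it reports no uncertainty. On the plan's own assumption for EGD, zero is the most likely count. A table entry of 0% with a standard error of 0 would suggest that the EGD rate is known exactly and is clearly below the rate for Cytosponge, when 40 subjects cannot show either. That would defeat the purpose the section gives for reporting precision.

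Willingness to repeat and first preference (secondary objectives 2 and 3) are to be computed as proportions with no test named, so the precision measure is the only uncertainty a reader would see for them.

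**Working it through.** **Inputs, all from Section 9.1.** High-score rates of 1% (EGD), 5% (Cytosponge) and 20% (TNE); n = 40, each subject assessed on each modality; correlation 0.3; Fisher's exact test at 0.05; stated power 80%.

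**The plan's own figure.** Simulating 20,000 trials with these rates and a 3 × 2 exact test gives power of 80.2% with independent outcomes, 81.0% with a latent correlation of 0.3, and 81.9% with a binary correlation close to 0.3 where that is attainable. The stated 80% is reproduced, so 1%, 5% and n = 40 are the working assumptions.

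**Chance of no high EGD scores.** P(0 of n) = (1 − p)^n. Only the EGD rate matters, so the within-subject correlation plays no part.

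| Assumed true EGD rate | P(0 of 40) |
|---|---|
| 1% (plan) | 0.99^40 = 66.9% |
| 2% | 0.98^40 = 44.6% |
| 5% | 0.95^40 = 12.9% |

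The last row is also the chance of a zero count for Cytosponge at its planned rate.

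**What would be tabulated at 0 of 40.**
- Plug-in standard error: √(p̂(1 − p̂)/n) = √(0 × 1/40) = 0. The true standard error at a 1% rate is √(0.01 × 0.99/40) = 1.57 percentage points.
- Wald 95% interval: 0 ± 1.96 × 0, that is 0% to 0%.
- Exact (Clopper-Pearson) upper limit: 1 − 0.025^(1/40) = 8.8%.
- Wilson upper limit: 1.96²/(40 + 1.96²) = 3.84/43.84 = 8.8%.

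Both sound intervals include the 5% assumed for Cytosponge.

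**Coverage of nominal 95% intervals at n = 40**, by summing exact binomial probabilities over the counts whose interval contains the true rate:

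| True rate | Wald | Wilson | Clopper-Pearson |
|---|---|---|---|
| 1% | 33.1% | 93.9% | 99.3% |
| 5% | 86.8% | 95.2% | 98.6% |

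At 1% the Wald interval misses whenever the count is zero, so its coverage cannot exceed 1 − 0.669 = 33.1%.

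**Separate cohorts.** Sizes are not stated, so the following are illustrations only, at the planned EGD rate of 1%:

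| Assumed cohort size | P(0 high EGD scores) | Exact 95% upper limit at zero |
|---|---|---|
| 30 | 74.0% | 11.6% |
| 20 | 81.8% | 16.8% |
| 10 | 90.4% | 30.8% |

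At an assumed n = 20, Wald coverage is 18% at a 1% rate and 64% at 5%.

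**The case against.** The strongest reply is that the plan prescribes nothing faulty. It names no standard error formula and no Wald interval, and it already permits an exact or Wilson interval without amendment. Its stated purpose arguably rules out a standard error of 0. This stands in part: the fault is an open choice, not an error written into the plan. But one of the two options offered fails in the likeliest EGD result, and choosing a confidence interval does not help if it is a Wald interval.

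A reader might infer more than the documents support:
- *That EGD will have no high scores, or that its table entry will be wrong.* This needs both a true rate near 1% and the choice of a plug-in standard error or Wald interval. The 1% is an uncited power assumption, and the chance of a zero count falls to 13% at a 5% rate.
- *That the main comparisons are invalid.* The planned Kruskal-Wallis and chi-square tests, the power figure and the sample size do not use these standard errors.
- *That EGD is the reference modality, or the high-score proportion the sole primary measure.* Section 9.1 describes a three-way comparison and gives both medians and proportions.
- *That every proportion is known to be affected.* The documents give no expected rate for willingness to repeat or first preference, so nothing can be computed for them. Using the same interval there is a matter of consistency.

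**Conclusion.** The point holds as a minor gap in the reporting rule. If the EGD rate is near the planned 1%, there is about a two-in-three chance of a zero count, and the permitted standard error or Wald interval would then show zero width where the data are compatible with rates up to 8.8%. Across nominal 95% intervals at n = 40, Wald coverage is 33% at a 1% rate and 87% at 5%, against 94% and 95% for Wilson. Separate cohort analyses would be worse, by an amount that depends on sizes the plan does not give.

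The conclusion rests on the plan's rates, on 40 evaluable EGD scores (with 36, the chance of zero rises to 0.99^36 = 69.6%), and on the usual plug-in formula being the one chosen. The effect is confined to how precision is displayed.

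**What to change.** In Section 9.1, state that the proportions with high IES scores, for each modality, overall and by cohort, will be reported with Wilson or Clopper-Pearson 95% confidence intervals, and not with a standard error or Wald interval alone. Choose one of the two methods before analysis. For consistency, use the same interval for willingness to repeat and first preference.

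The cost is one sentence and standard software, with no new data and no change in sample size. The downside is visibly wider intervals when counts are near zero (0% to 8.8% in place of 0% to 0% for 0 of 40). Clopper-Pearson is somewhat conservative, with coverage of about 99% at the two planned rates above; Wilson stays closer to 95%.

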10 STUDY MANAGEMENT

10.1 Institutional Review Board (IRB) Approval

IRB approval will be obtained prior to subject recruitment and enrollment. Research staff are responsible for maintaining IRB approval throughout the duration of the study, including submission of continuing review and modifications when appropriate per local IRB reporting requirements. In addition, research staff must ensure timely submission of any protocol amendments and obtain IRB approval prior to implementation of protocol amendments.

10.2 Required Documentation

Before the study can be initiated, the following documentation must be placed on file.

- A copy of the official IRB approval letter for the protocol and informed consent
- IRB membership list
- CVs and medical licensure for the principal investigator and any sub-investigators who will be involved in the study
- Investigator's signature documenting understanding of the protocol and providing commitment that this trial will be conducted according to all stipulations of the protocol

10.3 Data Management

The study principal investigator and study team will be responsible for study conduct and analysis. The study monitor will be responsible for source data verification.

10.4 Data Collection

Data collection is the responsibility of the study personnel at the site under the supervision of the principal investigator. The investigator is responsible for ensuring the accuracy, completeness, legibility, and timeliness of the data reported.

All source documents should be completed in a neat, legible manner to ensure accurate interpretation of data.

Hardcopies of study visit worksheets may be used as source document worksheets for recording data for each participant enrolled in the study. Data recorded in the electronic case report form (eCRF) derived from source documents should be consistent with the data recorded on the source documents. If source documentation is maintained in an electronic medical record, then electronic source is allowable if the system is 21 CFR 11 compliant, and access is provided to the monitor for clinical monitoring.

Study data (including adverse events, AEs), concomitant medications, and expected adverse reactions data) and clinical laboratory data will be entered into REDCap, a 21 CFR Part 11-compliant data capture system provided by UNC Chapel Hill. The data system includes password protection and internal quality checks, such as automatic range checks, to identify data that appear inconsistent, incomplete, or inaccurate. Study data will be entered directly from the source documents. Missing data will be noted in the database and the study team will provide reasons for missing data.

10.5 Adherence to the Protocol

A protocol deviation is any noncompliance with the clinical trial protocol. The noncompliance may be either on the part of the participant, the investigator, or the study site staff. As a result of deviations, corrective actions are to be developed by the site and implemented promptly.

It is the responsibility of the site investigator to use continuous vigilance to identify and report deviations in a timely manner after identification of the protocol deviation, or prior to the scheduled protocol-required activity. All deviations must be addressed in study source documents and reported to the reviewing Institutional Review Board (IRB) per their policies. The principal investigator is responsible for knowing and adhering to the reviewing IRB requirements.

Any deviations from the protocol identified will be documented on case report forms.

10.6 Noncompliance

Noncompliance is defined by the UNC IRB as intentional or unintentional failure to follow applicable federal regulations, the requirements or determinations of the IRB, the IRB-approved study protocol, or University policies. Noncompliance can occur as a result of performing an act(s) that violate(s) requirements. Noncompliance can also occur as a result of failing to act when required.

10.7 Unanticipated Problems Involving Risks to Subjects or Others

10.7.1 Definition

As defined by UNC's IRB, unanticipated problems involving risks to study subjects or others (UPIRSO) refers to any incident, experience, or outcome that:

- Is unexpected (in terms of nature, severity, or frequency) given (a) the research procedures that are described in the protocol-related documents, such as the IRB-approved research protocol and informed consent document; and (b) the characteristics of the subject population being studied;
- Is related or possibly related to a subject's participation in the research; and
- Suggests that the research places subjects or others at a greater risk of harm (including physical, psychological, economic, or social harm) related to the research than was previously known or recognized.

10.7.2 Reporting

Any UPIRSO that occurs during the conduct of this study and that meets the criteria must be reported to the UNC IRB using the IRB's web-based reporting system.

10.8 Definition of Adverse Events (AE)

An adverse event means any untoward medical occurrence associated with the use of an intervention in humans, whether or not considered intervention-related (21 CFR 312.32 (a)).

10.9 Adverse Event Assessment

A member of the study team will be present during all in-person visits during which Cytosponge, TNE and EGD will be administered to monitor safety and adverse event assessment. Participants will be assessed for adverse events during all in-person visits. All documented AEs will be addressed and followed until resolution and their resolution documented in the participant's research record. Local IRB guidelines for reporting adverse events will be followed. Only those AEs that meet UNC IRB criteria for reporting will be reported to the UNC IRB.

10.10 Severity of Event

For adverse events (AEs) the following guidelines will be used to describe severity.

- **Grade 1 (Mild)** – Events require minimal or no treatment and do not interfere with the participant's daily activities.
- **Grade 2 (Moderate)** – Events result in a low level of inconvenience or concern with the therapeutic measures. Moderate events may cause some interference with functioning.

- **Grade 3 (Severe)** – Events interrupt a participant's usual daily activity and may require systemic drug therapy or other treatment. Severe events are usually potentially life-threatening or incapacitating. Of note, the term "severe" does not necessarily equate to "serious."
- **Grade 4 (Life-Threatening)** – Life-Threatening consequences; urgent intervention indicated.
- **Grade 5 (Death)** – Death related to AE.

10.11 Relationship to Study Intervention

All adverse events (AEs) must have their relationship to study intervention assessed by the clinician who examines and evaluates the participant based on temporal relationship and his/her clinical judgment. The degree of certainty about causality will be graded using the categories below. In a clinical trial, the study product must always be suspect. Only those events that are definitely related or possibly related to participation in this research study will be reported.

- **Definitely Related** – There is clear evidence to suggest a causal relationship, and other possible contributing factors can be ruled out. The clinical event, including an abnormal laboratory test result, occurs in a plausible time relationship to study intervention administration and cannot be explained by concurrent disease or other drugs or chemicals. The response to withdrawal of the study intervention (dechallenge) should be clinically plausible. The event must be pharmacologically or phenomenologically definitive, with use of a satisfactory rechallenge procedure if necessary.
- **Possibly Related** – There is evidence to suggest a causal relationship, and the influence of other factors is unlikely. The clinical event, including an abnormal laboratory test result, occurs within a reasonable time after administration of the study intervention, is unlikely to be attributed to concurrent disease or other drugs or chemicals, and follows a clinically reasonable response on withdrawal (dechallenge). Rechallenge information is not required to fulfill this definition. "Possibly related" means there is a reasonable possibility that the incident, experience, or outcome may have been caused by the procedures involved in the research. Reasonable possibility means that the event is more likely than not related to participation in the research or, in other words, there is a >50% likelihood that the event is related to the research procedures.
- **Somewhat Likely to be Related** – There is some evidence to suggest a causal relationship (e.g., the event occurred within a reasonable time after administration of the trial medication). However, other factors may have contributed to the event (e.g., the participant's clinical condition, other concomitant events), so there is a <50% likelihood that the event is related to the research procedures. Although an AE may rate only as "somewhat likely to be related" soon after discovery, it can be flagged as requiring more information and later be upgraded to "possibly related" or "definitely related", as appropriate.
- **Unlikely to be Related** – A clinical event, including an abnormal laboratory test result, whose temporal relationship to study intervention administration makes a causal relationship improbable (e.g., the event did not occur within a reasonable time after administration of the study intervention) and in which other drugs or chemicals or underlying disease provides plausible explanations (e.g., the participant's clinical condition, other concomitant treatments).
- **Not Related** – The AE is completely independent of study intervention administration, and/or evidence exists that the event is definitely related to another etiology. There must be an alternative, definitive etiology documented by the clinician.

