administered sponge will be assessed post-procedure for signs of fracture or incomplete retrieval of the sponge, and in the unlikely case such incomplete retrieval occurs, the sponge will be retrieved during the routine care endoscopy which is scheduled to immediately follow administration of the sponge. If any potential bleeding is noted due to administration of the sponge, this will also be investigated, and, as necessary, treated during the routine upper endoscopy.

Transnasal Endoscopy (TNE) potential risks share the same risks as a conventional endoscopy (reported above). These include nasal discomfort; gagging (mild); discomfort during insertion; aspiration (drawing matter into the lungs along with the breath); bleeding; epistaxis (nosebleed); sinus infection; choking; nausea; retching or vomiting; anxiety; severe pain. A rare risk includes esophageal perforation (occurring in <0.1% of people, or less than 1 out of 10,000 people) which could possibly require surgery to repair.

The equipment for small-caliber endoscopy is FDA approved, and all study procedures will be carried out with trained and/or licensed qualified staff. In the case of procedural complications, the participating investigators will refer the patient for the appropriate care.

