10.14 Time Period and Frequency for Event Assessment and Follow-Up

The occurrence of an adverse event (AE) or serious adverse event (SAE) may come to the attention of study personnel during study visits and interviews of a study participant presenting for medical care, or upon review by a study monitor.

Only those events that are definitely related or possibly related to participation in this research study will be reported. All AEs will be captured on the appropriate case report form (CRF). Information to be collected includes event description, time of onset, clinician's assessment of severity, relationship to study device (assessed only by those with the training and authority to make a diagnosis), and time of resolution/stabilization of the event. All AEs will be followed to adequate resolution.

Any medical condition that is present at the time that the participant is screened will be considered as baseline and not reported as an AE.

Changes in the severity of an AE will be documented to allow an assessment of the duration of the event at each level of severity to be performed. AEs characterized as intermittent require documentation of onset and duration of each episode.

Events will be followed for outcome information until resolution or stabilization.

All new or worsening adverse events (AEs) will be collected for all subjects from the time of subject enrollment through study completion or termination of the clinical investigation.

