10.14.2 Adverse Event Documentation and Reporting

Research staff will maintain records of all adverse events and report them in a timely manner via completion of the Adverse Event Case Report Form. The form should be updated with any changes including updates to severity, relatedness, and resolution. Adverse events will be reported to the UNC IRB per UNC IRB reporting requirements.

Events will be described using the NCI Common Terminology Criteria for Adverse Events (CTCAE).

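### The relatedness rule in 10.11 and 10.14 will tend to keep harms that TNE and Cytosponge share with the same-day EGD out of what is reported, although they stay on the case report form

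*Combined protocol and SAP*

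**What the plan says.** Section 10.11 defines five causality grades and limits reporting to the top two: "Only those events that are definitely related or possibly related to participation in this research study will be reported". Section 10.14 repeats the sentence. Neither place names the recipient.

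- **Definitely related** requires other contributing factors to be excluded.
- **Possibly related** has two conditions: "There is evidence to suggest a causal relationship, and the influence of other factors is unlikely", and "there is a >50% likelihood that the event is related to the research procedures".
- **Somewhat likely** covers events to which other factors, including concomitant events, may have contributed, "so there is a <50% likelihood that the event is related to the research procedures". It is not a reported grade, though it may later be upgraded.

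Under 5.1 and 7.3, Cohort A has TNE immediately before EGD, and Cohort B has Cytosponge, then TNE, then EGD. The EGD is routine care with biopsy. Section 8.1 says of TNE: "Transnasal Endoscopy (TNE) potential risks share the same risks as a conventional endoscopy (reported above". It describes the EGD risks as not added by the study.

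On recording, 10.14 requires every adverse event on the case report form with onset, severity and "relationship to study device (assessed only by those with the training and authority to make a diagnosis". Section 10.14.2 adds: "Research staff will maintain records of all adverse events and report them in a timely manner", by completing the adverse event form. The synopsis, however, describes the follow-up call as collecting events related to participation. Section 9.1 plans no safety tabulation.

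**The concern.** A test that asks whether other causes are unlikely works when other causes are occasional. Here one is scheduled for every subject, often minutes after the research procedure, and it shares much of its risk profile. A clinician applying 10.11 literally to a sore throat or bleed noticed after EGD can rarely call the influence of EGD unlikely, so the event drops to a grade that is not reported. The omission then comes from the rule and runs in one direction.

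TNE is done only for research in every subject, and Cytosponge only for research in Cohort B. These are the procedures whose tolerability is under study. If their shared harms are mostly credited to routine EGD, the reported harm of the research procedures is too low.

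**Working it through.** The plan gives no figure for this point, so there is nothing to reproduce. The check asks when a shared harm, first seen during or after EGD, meets the two conditions for possibly related.

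**Likelihood condition.** As a rough guide, the share attributable to research is s = r / (r + e). Here r is the summed risk of the research procedures that carry the harm, and e is the EGD risk. EGD is treated as the non-research cause, in line with 8.1.

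*Common shared harms.* The documents give no rates. Assume each research procedure carries k times the EGD risk:

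| k | Cohort A: k/(1+k) | Cohort B, harm shared by all three: 2k/(1+2k) |
|---|---|---|
| 0.5 | 0.5/1.5 = 33% | 1/2 = 50% |
| 1 | 1/2 = 50% | 2/3 = 67% |
| 2 | 2/3 = 67% | 4/5 = 80% |

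With equal risks, Cohort A does not exceed 50%, and Cohort B does.

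*Perforation (8.1).* EGD is about 3 in 10,000. TNE is given two upper bounds that differ tenfold: below 1 in 10,000, and below 0.1% (10 in 10,000).

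- At 1 in 10,000: 1/(1+3) = 25%, not reportable.
- At 10 in 10,000: 10/(10+3) = 77%, which passes this condition.
- Break-even: the TNE risk would have to exceed 3 in 10,000.

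Because the TNE figures are bounds, 25% and 77% are themselves upper limits.

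*Aspiration (8.1).* EGD is 8 in 10,000, and no TNE figure is given. In Cohort A the TNE risk would have to exceed 8 in 10,000.

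**Other-causes condition.** This applies whatever the percentage. At 67% in Cohort B, one third of the attribution still lies with EGD, which is hard to call unlikely. At 77% for perforation the remainder is 23%. So an event can pass the first condition and still fail the second.

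**How often serious events would arise.** The chance of at least one in 40 subjects is 1 − (1 − p)^40:

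- EGD perforation, p = 0.0003: 1.2%
- TNE perforation, p = 0.0001 to 0.001: 0.4% to 3.9%
- EGD aspiration, p = 0.0008: 3.2%

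In practice the rule will therefore act mainly on mild shared events such as sore throat, gagging and minor bleeding.

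**Events the rule does not suppress.** Nasal discomfort, epistaxis and sinus infection are listed for TNE but not for EGD, and sponge detachment is specific to Cytosponge. Events that begin before EGD, including during the wait of at least two hours after Cytosponge (5.1), cannot be caused by that EGD.

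**The case against.** The strongest reply is that nothing is lost. Section 10.14 follows the restrictive sentence directly with the requirement to capture every event, with onset time and relatedness, and it collects all new or worsening events to study completion. Under 10.9 a study team member attends all procedures. The plan can be read as two tiers: record everything, escalate a subset. On that reading 10.14.2 does not contradict 10.11, because its reporting is done through the adverse event form. Grading also rests on clinical judgment of the individual case, and a somewhat likely event can be upgraded.

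Most of this stands, and it rules out several stronger readings that a reader might infer:

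- *That harms of TNE and Cytosponge in general go unreported.* Procedure-specific and pre-EGD events can qualify, and Cohort B can pass the 50% condition.
- *That the IRB or the publication will see a falsely clean record.* Sections 10.9 and 10.14.2 tie IRB submission to UNC IRB criteria that are not fully given, and nothing limits the publication to reported events.
- *That a TNE harm in Cohort A has no field on the form.* The case report forms are separate documents (Section 7). The text shows only that the term study device is singular and undefined.
- *That the perforation figures prove exclusion.* They run from 25% to 77%, rest on upper bounds, and apply population rates to single cases.

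What the reply does not meet is the rule itself. The two conditions are stated, the competing cause is scheduled, and upgrading needs information that procedures done in one session may never yield. Capture helps only if the captured events are later shown, and 9.1 does not say that they will be. The synopsis wording for the follow-up call also leaves unclear whether capture is complete after discharge.

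**Conclusion.** The point holds for a defined group: harms shared with EGD that emerge during or after it. For these, 10.11 and 10.14 bias the reported harm of TNE, and of Cytosponge in Cohort B, downward. The direction is clear, but the size cannot be fixed from the documents. The research share of a common shared event runs from 33% to 67% in Cohort A and from 50% to 80% in Cohort B over the assumed risk ratios of 0.5 to 2, so the other-causes condition often decides the grade. In 40 subjects the practical effect falls mainly on mild events, which still matter in a study of how procedures are tolerated. The conclusion assumes that EGD counts as a non-research cause and that 10.11 is applied as written. The events themselves remain recoverable from the case report forms. This merits a wording amendment. It is not evidence that safety data will be lost.

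**What to change.** 1. In 10.11 and 10.14, grade relatedness separately for Cytosponge, TNE and EGD in place of the single study device.
2. State that an event that cannot be separated from the same-day EGD counts as possibly related to the research procedure or procedures sharing that risk, and that this takes precedence over the two conditions in the definition.
3. Name the recipient of what is reported in 10.11 and 10.14. Reconcile those sentences with the capture requirement in 10.14, with 10.14.2, and with the synopsis description of the follow-up call.
4. Add to Section 9.1 a tabulation of all captured adverse events by procedure and onset time, regardless of causality grade. IRB submission continues to follow UNC IRB criteria.

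The cost is wording changes, two extra fields on the adverse event form (three grades in place of one), and a few more minor events listed. No study procedure changes.
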